7.1.12. Electrocardiogram

A single standard, 12-lead electrocardiogram (ECG) will be obtained as specified in the Schedule of Assessments (Table 1). Assessed ECG parameters will include heart rate and PR, QRS, QT, and QT corrected for heart rate (QTc) intervals. QT will be corrected using Fridericia's (QTcF) formula. ECGs will be performed after the subject has been resting in supine or semi-supine position for at least 5 minutes. When an ECG is scheduled at the same time as a blood sampling, the ECG reading should be obtained before the scheduled blood sampling. The ECG results will be interpreted at the site by a medically qualified person. If indicated, the ECG must be evaluated by a cardiologist or qualified internist.

7.1.13. Clinical Laboratory Assessments

Clinical laboratory tests will be performed as specified in the Schedule of Assessments ([Table 1](#)). Additional tests may be performed as clinically indicated.

Clinical laboratory parameters ([Table 2](#)) to be obtained include:

- Hematology, chemistry, and urinalysis assessments
- Coagulation (Partial thromboplastin time, Prothrombin time, and INR) assessments
- Thyroid function tests (thyroid stimulating hormone, free triiodothyronine, and free thyroxine) for clinical signs and symptoms of thyroid disorder
- Autoimmune panel
- Adrenal function tests, if indicated

NOTE: At Screening, subjects assessed as at risk for adrenal insufficiency should undergo diagnostic tests for ACTH and morning cortisol, and/or high-dose ACTH stimulation test (preferred testing method), if clinically indicated, via local laboratory.

- HIV, Hepatitis C/B, if indicated

A central laboratory will be used for clinical laboratory safety assessments; local laboratories may be used for eligibility and treatment decisions. The central laboratory will provide collection supplies and perform analysis of clinical laboratory evaluations. Specimens will be appropriately processed, and laboratory reports will be provided to the Investigator. A summary of the number and volume of laboratory specimens collected at each study visit is provided in [Appendix B](#).

The Investigator is responsible for reviewing central laboratory results and assessing all out-of-range findings as either clinically significant or non-clinically significant. Clinically significant laboratory results should be recorded in the eCRF as medical history if before CMP-001 dosing at W1D1, or as AEs following CMP-001 dosing at W1D1.

Table 2: Clinical Laboratory Assessments

Hematology	Serum Chemistry	Urinalysis	Other Laboratory Tests
Red blood cells (RBCs)	Alanine aminotransferase	Blood	Coagulation:
White blood cells (WBCs)	Albumin	Glucose	PTT
Differential WBC count	Alkaline phosphatase	Nitrites	PT
Hemoglobin	Amylase	pH	INR
Hematocrit	Aspartate aminotransferase	Protein	
Platelets	Bilirubin	Specific gravity	Thyroid Function Studies:
	Blood urea nitrogen	WBCs	Thyroid stimulating hormone, Free T3, Free T4
	Calcium		
	Chloride	Microscopic Battery:	Autoimmune Laboratory Panel:
	Creatinine	RBCs, WBCs, epithelial cells, casts	Anti-dsDNA, anti-nuclear antibody, anti-neutrophil cytoplasmic antibody, rheumatoid factor, and antibodies to ribonucleoprotein (anti-RNP)
	Glucose	(only if significant positive findings on urinalysis)	
	Lactate dehydrogenase		Tests to be performed as clinically indicated:
	Lipase		Human immunodeficiency virus
	Phosphorous		Hepatitis B and C
	Potassium		
	Sodium		
	Total protein		

Abbreviations: dsDNA = double-stranded DNA; INR = international normalized ratio; PT = prothrombin time; PTT = partial thromboplastin time; RBC = red blood cell; RNP = ribonucleoprotein; T3 = triiodothyronine; T4 = thyroxine; WBC = white blood cell.

NOTE: Refer to the Study Laboratory Manual for additional information.

Retesting of laboratory parameters and/or other assessments within any single Screening or Lead-in period will be permitted (in addition to any parameters that require a confirmatory value). Laboratory parameters and/or assessments that are included in the Schedule of Assessments (Table 1) may be repeated in an effort to find all possible well-qualified participants. Consultation with the Medical Monitor may be needed to identify whether repeat testing of any particular parameter is clinically relevant.

7.1.14. Pregnancy Testing

Pregnancy testing will be performed on WOCBP at the time points specified in the Schedule of Assessments (Table 1). A serum pregnancy test is required during screening. A serum or urine pregnancy testing will be completed for time points after Screening.

A WOCBP must have a negative serum or urine pregnancy test (minimum sensitivity 25 IU/L or equivalent units of human chorionic gonadotropin) within 24 hours before the start of study treatment. An extension up to 72 hours before the start of study treatment is permissible in situations where results cannot be obtained within the standard 24-hour window.

If a urine pregnancy test is positive at any time point, the test must be confirmed with a serum sample. If a serum pregnancy test is required based on a positive urine pregnancy test, serum test results must be confirmed as negative before enrollment or subsequent treatment of the subject. If the serum test confirms the subject is pregnant, they must have the EOT visit, and the pregnancy must be reported to the Medical Monitor.

7.2. Disease Assessments

Disease assessments (radiographic and CNS imaging) will be collected according to the Schedule of Assessments ([Table 1](#)). Acceptable assessment methods, definition of measurable disease, and selection of target and non-target lesions will be defined by RECIST v1.1 (see [Appendix D](#)).

The same disease assessment method(s) used to confirm eligibility during Screening (CT, MRI) should be used throughout the study for all disease assessments. Changes in imaging modalities may be acceptable with Medical Monitor approval if required for the subject's safety. All scans should be performed at least 2 weeks after the previous CMP-001 IT injection to prevent detection of injection-related pseudoprogression.

Photographic and/or radiographic images demonstrating disease progression on prior PD-1-blocking antibody treatment will be collected whenever available.

All disease assessments will be evaluated by the Investigator according to RECIST v1.1 ([Appendix D](#)) and iRECIST ([Appendix E](#)).

7.2.1. Radiographic Imaging

Contrast-enhanced CT and MRI are the only acceptable radiographic imaging modalities for disease assessment. Contrast-enhanced CT imaging is required when contraindications are not present. Contrast-enhanced CT assessments may be combined with positron emission tomography (PET) as long as disease status can be thoroughly assessed. Ultrasound imaging may be used for measurement of lesions for itRECIST ([Appendix F](#)).

A target lesion(s) not intended for intratumoral (IT) injections should be clearly labeled in the Baseline imaging.

7.2.2. Photographic Imaging

Digital photographs of visible CMP-001-injected and non-injected skin lesions should be taken at Baseline and if a clinically relevant change occurs. As part of disease assessment, photos should be taken at the same intervals as the radiographic imaging. These photographs will be utilized to demonstrate response in visible tumors. Photos should be taken with a digital camera of adequate resolution. To clearly capture the morphology of the tumor, both the skin lesion and the surrounding tissue should be included in the field of view. Care should be taken to ensure subject privacy. Each lesion should be clearly labeled with a unique identifier which must be used throughout the trial. A metric ruler must also be included in the photograph field of view as a size reference. Photographic imaging will be collected by the site staff and uploaded to the central image repository.

A target lesion(s) not intended for IT injections should be clearly labeled in the Baseline imaging.

If a CR is observed, sites should continue to obtain confirmation photographs according to the Schedule of Assessments ([Table 1](#)).

Refer to the photographic imaging guideline for further guidance.

7.2.3. Central Nervous System Imaging

Baseline brain imaging by contrast-enhanced CT or MRI (per site local standards) should be provided at Screening for subjects with known or suspected brain metastases. On-study brain

imaging is only required for subjects with current or prior history of brain metastases or clinical signs or symptoms of CNS disease.

The same modality of brain imaging should be utilized throughout the study for an individual subject.

7.2.4. On-Treatment Disease Assessment

On-treatment disease assessments will be collected per the time points specified in the Schedule of Assessments ([Table 1](#)).

Because the volume from the IT injection of CMP-001 and related inflammation may cause a tumor to transiently enlarge leading to an inaccurate assessment, disease imaging that includes a lesion injected with CMP-001 should not be performed within 2 weeks after the injection unless medically necessary.

7.2.5. Treatment and Disease Assessment Beyond Progressive Disease

Clinically stable subjects may continue to be treated beyond RECIST v1.1 progression at the Investigator's discretion. Subjects who receive study treatment beyond PD per RECIST v1.1 will have subsequent disease assessments evaluated using iRECIST by the Investigator.

Clinically stable subjects may continue to be treated beyond RECIST v1.1 progression at the Investigator's discretion until PD is confirmed according to iRECIST. Treatment beyond progression is permitted only in subjects who are clinically stable ([Seymour, 2017](#)). An assignment of clinical stability requires that no worsening of performance status has occurred, that no clinically relevant increases in disease-related symptoms such as pain or dyspnoea occur that are thought to be associated with disease progression, and that no requirement for intensified management of disease-related symptoms exists, including increased analgesia, radiotherapy, or other palliative care. Disease assessments should continue according to the Schedule of Assessments ([Table 1](#)).

7.2.6. Confirmation of Response

Subjects with a CR or PR per RECIST v1.1 or iCR or iPR per iRECIST must have a confirmatory assessment performed at least 4 weeks after the initial response. All scans should be performed at least 2 weeks after the previous CMP-001 IT injection to prevent injection-related pseudoprogression.

Subjects with an iCR or iPR per iRECIST must also have a confirmatory assessment performed at least 4 weeks after the initial assessment where response was declared by the Investigator.

Once confirmed, subsequent assessments should continue according to the Schedule of Assessments ([Table 1](#)).

7.3. Translational Assessments

7.3.1. Collection of Blood for Translational Biomarker and Pharmacokinetics Analyses

Blood samples, including serum and/or plasma will be collected for exploratory biomarker and pharmacokinetic assessments as specified in the Schedule of Assessments ([Table 1](#)). The procedures for sample collection, processing, storage, and shipment are provided in the Laboratory Manual. Blood samples will be tested to determine concentration of CXCL10 and other cytokines before and during treatment with CMP-001 to

evaluate association with the observed clinical responses to study treatment. Samples may be used for additional exploratory analysis of biomarkers thought to play a role in head and neck cancer, cancer immunotherapy, or TLR9, including but not limited to concentration of serum/plasma analytes. These findings may be analyzed for association with observed clinical responses to the combination of CMP-001 and pembrolizumab, and subsequent exploration of factors associated with response or resistance to CMP-001 in combination with pembrolizumab. These samples may be also used for research to develop methods, assays, prognostics and/or companion diagnostics related to TLR9 agonism and cancer immunotherapy.

7.3.2. Collection of Tumor Biopsies for Translational Assessments Analyses

Fresh tumor biopsy samples are mandatory, if safe and medically feasible, at Screening or within 90 days (before W1D1) and W7D1 before CMP-001 IT injection, as specified in the Schedule of Assessments ([Table 1](#)). If the Investigator believes it is unsafe to perform a biopsy, the subject may be considered eligible for study enrollment after discussion with the Medical Monitor. The decision and rationale to forego biopsy samples should be clearly documented. Archival tumor biopsy samples should also be collected during Screening, if available.

Tumor biopsies will be used to assess PD-L1 expression and may be used to analyze tumor immune cell infiltrates, such as CD3+CD8+ T-cells. Biopsies may be used for additional exploratory analysis of biomarkers thought to play a role in head and neck cancer, cancer immunotherapy, or TLR9, including but not limited to techniques such as the Nanostring IO360 panel evaluating 46 RNA gene expression signatures, and may be used to determine the presence of DNA mutations associated with tumor resistance. These findings may be analyzed for association with observed clinical response, resistance and/or adverse events to the combination of CMP-001 and pembrolizumab.

Determination of PD-L1 status is mandatory. If tumor PD-L1 status has been obtained before study entry, this value and method (detection antibody) will be recorded in the eCRF. If tumor PD-L1 status has not been obtained before study entry and archival tissue is available, it should be obtained from the archival biopsy sample at Screening. The PD-L1 value will be recorded in the EDC.

Additional tumor biopsies may be collected at other time points at the discretion of the Investigator.

7.3.3. Collection of Blood Samples for Cytokine and Complement Assessment

Blood samples are to be collected at the time points specified in the Schedule of Assessments ([Table 1](#)). When possible, samples should be collected at the time that any AEs of cytokine release syndrome are experienced.

7.4. Safety Assessments

Safety will be assessed on an ongoing basis throughout this study. All safety assessments and AEs will be recorded on the appropriate eCRF and reported to the Sponsor or its representatives (as applicable). Medical occurrences that begin before the start of study treatment administration but after obtaining informed consent will be recorded on the Medical History/Current Medical Conditions section of the eCRF, not the AE section. All treatment-emergent adverse events (TEAEs), defined as an AE that started or worsened in severity on or after the date of Informed Consent, will be graded according to CTCAE

version 5.0 ([Appendix C](#)) and coded using the Medical Dictionary for Regulatory Activities (MedDRA). Worsening TEAEs (i.e., increase to higher severity/grade) should be recorded as new AEs. Ongoing AEs with a decrease in severity/grade do not need to be captured as new AEs.

Abnormal vital sign measurements, clinical laboratory test results, and/or physical examination findings deemed clinically significant by the Investigator may be repeated, until the value returns to Baseline, within normal limits (WNL), or reaches a clinically stable endpoint, as determined by the Investigator. Any post-Baseline abnormal findings that are considered clinically significant by the Investigator will be recorded on the AE page of the eCRF. The Investigator is responsible for reviewing all clinical laboratory results.

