8.1.3. Definition of a Treatment-Emergent Adverse Events

A TEAE is defined as an AE that started or worsened in severity on or after the date that study drug was first administered (W1D1) until 30 days after the last dose of study treatment.

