8.3. Procedures for Recording and Reporting Adverse Events

The Investigator is required to report to the Sponsor or its representatives all AEs that occur during the clinical trial (Title 21 Code of Federal Regulations [CFR] Part 312.64[b] and ICH E6 entitled “Guideline to Good Clinical Practice”) (ICH E6). At each study visit, subjects will be evaluated for new AEs and the status of existing AEs. TEAEs observed from the time of consent until 30 days after the last dose of study drug (both CMP-001 and pembrolizumab) are to be recorded on the AE page of the eCRF.

The date, time of onset, resolution, determination of seriousness, severity, action taken, outcome and relationship to CMP-001 and pembrolizumab will be recorded for all AEs. AEs starting more than 30 days after the last dose of study drug should not be recorded on the AE eCRF unless they are considered to be related to study treatment.

All AEs and SAEs experienced by a subject will be recorded on the appropriate eCRF. In addition, for all SAEs a paper SAE Report Form will be completed and submitted to IQVIA Biotech Safety preferably via email to: [REDACTED] or by fax to [REDACTED]

[REDACTED] as back up within 24 hours of awareness. Information including a detailed description of the event; date and time (24-hour clock) of event onset and resolution; determination of seriousness, severity, corrective treatment, outcome, relationship to study drug; and action taken regarding the study drug will be recorded. Vital signs, laboratory results, and other safety assessments noted in Section 7.4 will be recorded as AEs if they are determined to be clinically significant findings in the opinion of the Investigator. When possible, a diagnosis should be recorded as an AE, rather than symptoms or isolated laboratory abnormalities related to the diagnosis. A medical or surgical procedure is not an AE; rather the condition leading to the procedure should be recorded as the AE. If the condition is not known, the procedure must be recorded as an AE instead. Similarly, death is not an AE, but is rather the outcome of the AE(s) that resulted in death. If the AE(s) leading to death are not known, then death must be reported as an AE.

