8.3.1. Reporting Serious Adverse Events

All SAEs and associated source documents must be reported in written or typed English via completion of the eCRF AE page and accompanying paper SAE Report Form to IQVIA Biotech Safety (following the same reporting process outlined in Section 8.3) within 24 hours of first knowledge of the event regardless of relationship to the study procedures or individual study drugs. The paper SAE Report form should be used to record pertinent information,

regarding the SAE. The Investigator is requested to supply as much detailed information as possible regarding the event at the time of the initial report.

SAEs will be collected from the time of consent until 30 days after the last dose of any study allowed drug treatment.

If at any time after the subject has completed participation in the study, the Investigator or study staff becomes aware of an SAE during the study reporting period that they believe is possibly, probably, or definitely related to either study drug (see Section 8.2.2), then the event and any known details must be reported promptly to the Sponsor or its representatives. The following reporting instructions must be followed.

At minimum, the Investigator will be asked to provide the following information:

- For the initial SAE notification, the Investigator must provide, at a minimum, basic information such as the protocol number, subject's year of birth or age at onset, subject identification (ID) number, period of study drug intake, event term, nature of the event, detailed description of the clinical course of the event, seriousness criteria, causality of the event to CMP-001 and pembrolizumab separately, and severity.
- In addition, the initial SAE information entered on the eCRF and paper SAE Report Form should include all pertinent known information about the SAE and the affected subject, such as the following: subject sex; description of the AE including reason for assessment as serious, and individual study drug information including doses, dates of dosing, and action taken with individual study drugs.

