Adverse event (AE) data are available to the Sponsor from two sources, the eCRFs and the Serious Adverse Event (SAE) paper forms and corresponding SAE narratives. While reconciliation will be performed to ensure consistency between the two types of data, the production of data summaries and listings will be based on the data collected on the eCRF.

Treatment-emergent adverse event (TEAE)

Pretreatment AEs are AEs that occur from the time of informed consent up to the first dose of study treatment (W1D1). A treatment-emergent adverse event (TEAE) is defined as an AE that started or worsened in severity on or after the date that study treatment was first administered (W1D1) until 30 days after the last dose of

Regeneron Pharmaceuticals Inc. / Protocol: CMP-001-007
IQVIA Biotech (Confidential) Project # SZA56629

study treatment. AE data collection also ceases at the time a new cancer treatment is started per protocol section 8.3, whichever occurs first.

Treatment-emergent adverse events will be coded using MedDRA (version 23.1) and data will be summarized for the Treated Analysis Set. The number and percent of subjects reporting each TEAE will be summarized, as well as the number of TEAEs. A subject with 2 or more TEAEs within the same level of summarization (i.e., system organ class or preferred term) will be counted only once in that level using the most severe event or most related (for the relationship to study treatment tables).

AEs are graded using Common Terminology Criteria for Adverse Events (CTCAE) Version 5.0. AE summaries may include summaries for all AEs and by the maximum CTCAE grade for the item being summarized (i.e., SOC or PT). In these cases, the outputs will include a row for All Grades as well as rows for the 5 potential CTCAE grades: Grade 1 (Mild), Grade 2 (Moderate), Grade 3 (Severe), Grade 4 (Life threatening or disabling), or Grade 5 (Death).

If grade is missing for a TEAE, the event will be counted as grade 3=severe in the TEAE summary tables. If relationship is missing for a TEAE, the event will be counted as related in the TEAE summary tables. Therefore, related AEs include those which are definitely, probably and possible related and those with missing relationship.

A TEAE summary table will be generated including the following (N (%)):

- Subjects with TEAEs
- Subjects with TEAEs of grade 3 or higher
- Subjects with TEAEs Related to CMP-001 and/or Pembrolizumab
- Subjects with CMP-001-related TEAEs

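### Treatment-emergence and pre-dose recording rules conflict, so harm from a post-consent screening procedure may be filed as Medical History, and no AE or SAE summary is designated for it

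*Protocol*

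**What the plan says.** On when treatment emergence begins, the Protocol gives two answers. Section 7.4 counts an event "defined as an AE that started or worsened in severity on or after the date of Informed Consent". Section 8.1.3 counts one that "started or worsened in severity on or after the date that study drug was first administered (W1D1"). Section 8.3 sides with consent in its wording: it sends "TEAEs observed from the time of consent until 30 days after the last dose of study drug" to the AE page. SAP IX.B agrees with 8.1.3 and uses events that "started or worsened in severity on or after the date that study treatment was first administered (W1D1").

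On where an event between consent and first dose is recorded, the documents also divide. Protocol 7.4 says that occurrences beginning before treatment "but after obtaining informed consent will be recorded on the Medical History/Current Medical Conditions section of the eCRF, not the AE section". SAP IX.B repeats that routing. Against this, Protocol 8.3.1 states: "SAEs will be collected from the time of consent until 30 days after the last dose of any study allowed drug treatment". It requires both the eCRF AE page and a paper SAE form within 24 hours. Protocol 7.4.1 has pretreatment AEs related to study procedures monitored from consent to W1D1. SAP IX.B itself sets up a category for these events: "Pretreatment AEs are AEs that occur from the time of informed consent up to the first dose of study treatment (W1D1").

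**The concern.** Screening procedures done after consent are part of the study, so harm from them belongs in its safety record. The example that matters most here is a fresh tumor biopsy. If a complication is entered as Medical History, it looks like a pre-existing condition and not an event the study caused. Two sites following different sections may record the same event on different pages, and the SAP builds its AE summaries and listings from the eCRF. The page chosen at the site therefore decides what can be reported. For subjects who fail screening there is no first dose at all, so a definition anchored on dosing never picks them up.

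**Working it through.** No power or sample-size figure is involved. The check sets the rules side by side and then follows one event through them.

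| Place | TEAE start | Record of an event between consent and first dose |
|---|---|---|
| Protocol 7.4 | Consent | Medical History, not the AE page |
| Protocol 7.4.1 | Not stated | Procedure-related AEs monitored; page not named; refers to 8.3 |
| Protocol 8.1.3 | First dose | Not stated |
| Protocol 8.3 | Consent, by its wording | AE page |
| Protocol 8.3.1 | Not applicable | SAEs: AE page plus paper form |
| SAP IX.B | First dose | Medical History, yet pretreatment AEs are defined |

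**Step 1: can the rules be followed together?** No. Within Protocol 7.4 itself, adjacent sentences make a post-consent, pre-dose event a TEAE and also bar it from the AE page. For a serious event, 7.4 bars the page that 8.3.1 requires.

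**Step 2: does SAP precedence settle it?** Only in part. SAP I.B says the SAP governs the analysis where the documents differ. That fixes first dose as the TEAE start for the tables. It does not tell a site which eCRF page to use, and the SAP's own sentence repeats the Medical History routing.

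**Step 3: where does a complication starting after consent and before W1D1 end up?**

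- Non-serious, filed under 7.4: Medical History only. For treated subjects it then appears in the Medical History table and listing (SAP VII.A), misclassified. It reaches no AE output.
- Non-serious, put on the AE page under 8.3: eligible for the by-subject AE listing, which SAP IX.B does not limit to TEAEs. No table is assigned to it.
- Serious, filed under 8.3.1: eligible for the AE and SAE listings. The SAP overview row counts only treatment-emergent SAEs. The SAE tables by system organ class stand under a heading for TEAE summaries, so their scope is at best ambiguous. Protocol 9.6.1 names an SAE table without that qualifier.
- Serious, but filed under 7.4: absent from the SAE listing unless reconciliation with the paper form catches it.
- Worsening on or after W1D1: a TEAE under every definition, and tabulated if recorded as an AE.

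**Step 4: who is outside the tables whatever page is used?** SAP II.C gives 39 screened = 15 screen failures + 24 treated. SAP IX uses the Treated Analysis Set, and Protocol 9.6.1 uses the Safety Analysis Set, which by 9.2.2 contains dosed subjects only. SAP VI.I uses the All-Screened set for disposition alone. So 15 of 39 subjects (15/39 = 38%) are outside every AE and SAE table. Their Medical History is not summarised either, because SAP VII.A uses the Treated set.

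**Step 5: how long is the window?** Protocol Table 1 places Screening at Day -30 to Day -1, so up to 30 days per subject.

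**The case against.** A reader might infer that these events appear in no AE or SAE output at all. The documents do not support that. SAP VI.K plans listings of all recorded data unless stated otherwise, and the AE and SAE listings in IX.B carry no TEAE restriction. Serious events also have an explicit route in Protocol 8.3.1, and an SAE summary under Protocol 9.6.1 could include those in treated subjects.

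Other strong readings fail too:

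- That reconciliation between SAE forms and the eCRF will fail. SAP IX.B plans it, and a paper form with no matching AE entry is the mismatch it should detect. What it lacks is an agreed answer on which page is right.
- That Protocol 7.4.1 captures AEs only after enrollment. It says all AEs are captured from then, which can be read as a tiered rule: procedure-related AEs before, everything after.
- That all 39 subjects underwent a mandatory on-study biopsy. Protocol 7.3.2 requires it only where safe and medically feasible and accepts one within 90 days before W1D1; inclusion criterion 4 accepts archival tissue. A complication that began before consent is outside the collection window.
- That TEAE incidence in the SAP tables is wrongly defined. The SAP uses first dose consistently for that purpose.

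It is also fair to say that the study is descriptive, has 24 treated subjects and is closed to enrollment, so rewording the Protocol cannot change how completed screening events were entered. That limits the value of the wording changes. It leaves the contradiction itself, the absence of a designated summary and the exclusion of screen failures from the tables standing.

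**Conclusion.** Wrong as written. The TEAE start conflicts between Protocol 7.4 (and the wording of 8.3) and Protocol 8.1.3 with SAP IX.B. The Medical History rule in Protocol 7.4 and SAP IX.B contradicts 8.3 and 8.3.1, and sits badly with 7.4.1 and with the SAP's own pretreatment category. A study-procedure complication before first dose may be filed as Medical History; if it is recorded as an AE it can be listed but has no designated summary. Events in the 15 screen failures reach no AE or SAE table.

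The size cannot be stated as a number of events, since neither document gives a rate. The 39 screened subjects and the 30-day window are upper bounds, and fewer subjects may have had a biopsy after consent. The conclusion assumes that the TEAE heading and the Treated set in the SAP are applied as written. It concerns completeness of safety reporting and leaves the efficacy analysis untouched.

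**What to change.** - **Protocol 7.4 and 8.3:** use one TEAE start, first dose, as in 8.1.3 and the SAP. Section 7.4 can point to 8.1.3 instead of defining the term again.
- **Protocol 7.4 and SAP IX.B:** state that SAEs and procedure-related AEs from consent to first dose go on the AE page, and that other pre-dose findings go to Medical History. This fits 8.3.1 and 7.4.1 as they stand; align 8.3 with it.
- **Data:** because screening is complete, query Medical History entries dated between consent and W1D1, or between consent and screen failure, and reconcile them with the paper SAE forms.
- **SAP IX.B:** add one listing of pretreatment procedure-related AEs and SAEs for the All-Screened Analysis Set, kept out of TEAE incidence.

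The cost is wording in three sections, one listing and a limited query. With the last subject enrolled on 22 June 2022, the query and the listing carry most of the benefit. Protocol 10.2 provides for only limited data on screen failures, so the query should first establish what was collected for them.
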